improvement toolkits that are common to both intervention conditions to all agencies/programs. Each conference is followed by planning and training for the intervention condition, followed six months later by client screening and recruitment of depressed patients into a panel study with baseline and 6- and 12-month measures. Administrators in all agencies and clinicians in sites participating in the trial, as well as some sites not in the trial, will complete an 18 month follow-up survey. After several months of collaborative analysis involving community agency partners, the project will sponsor a community feedback conference to share the outcomes findings and provide assistance in use of intervention materials based on evidence for their effectiveness. Final analyses and feedback conference will occur in the last year of the study.

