
each community and were typically more intensive than outlined above, such as having more training sessions, opportunities for make-ups, and more intensive supervision).

CEP Implementation: Agency intervention leaders, supported by study clinicians will train the unit clinicians/case workers in delivering PIC/WE Care protocols and provide consultation and supervision. The council will provide oversight, reviewing monthly reports from lead administrators and intervention experts, with feedback to unit leaders and intervention experts. These meetings will follow the CEP model for inclusiveness and fairness/respect and include grass-root community member perspectives supported by HAAF, QueensCare and Behavioral Health Services, the lead community-based agencies. The monthly reports from intervention leaders will describe progress, problems encountered. As clients are enrolled, program administrative staff will be notified, with client permission. Support for use of depression treatments will be encouraged for 6-12 months at the client level as in PIC. *(NOTE: The training model for this condition was modified with community input to be joint training by study experts and community leaders. We note that the design calls for notification of programs about client enrollment in CPIC but not RS programs).*

Community Feedback Conference: The lead CBOs will sponsor a Community Feedback Conference at 40 months (after all client outcomes data are collected), inviting all CPIC agencies as well as civic leaders and community members. The overall study council co-chairs will review outcomes findings, implementation stories, and council recommendations. Break out groups will discuss implications for implementing and sustaining depression services in the community. All participating agencies will be supported in having access to and using the study's intervention materials. *The toolkits and other intervention features for CEP and RS are summarized in Table 2.*

Table 2. Community Partners in Care Interventions and Training Features by Condition		
	Resources for Services (RS)	Community Engagement and Planning (CEP)

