Agencies/units assigned to community engagement implementation will participate in 4 months of planning and training for use of PIC/WE Care and to design an approach to fit the programs to their resources, priorities, and sites, with support of community members serving as co-intervention planners. Then they will participate in 12-18 months of implementing PIC/WE Care, including training the clinicians within participating units and supporting access to evidence-based treatment treatments for depressed clients enrolled into a client study. Those assigned to low-intensity, standard dissemination will attend a conference and have access to PIC toolkits on a website, but will not be asked to participate in other intervention planning or implementation at that time. Agencies/units in both conditions will be asked to participate in client enrollment within each unit, designed to achieve screening of a defined client pool for depression and enrollment of several depressed clients for each unit into baseline surveys and 6-month and 12-month follow-up surveys. In community-engagement practices, those clients will be identified to the practice so that they can initiate PIC/WE Care intervention activities to facilitate access to evidence-based depression treatments, following the approach developed within their implementation planning period. Following the 6-month outcomes data collection for the client study, the agencies in the community engagement condition will be asked to identify representatives to participate in collaborative analyses and preparation of findings for presentation at the Community Feedback Conference, attended by all participating Agencies, to

formulate recommendations for the field and for future community implementation, and initiate wait-list training for controls.

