Community Leaders and Advisors: For intervention groups, key agency leaders participate in the 4-month implementation planning, serve as leaders in the community conferences, help provide oversight during implementation, and participate in the collaborative analyses of data from each stage. Along with agency leaders, we will include community members who will serve as key community advisors, representing the community voice outside of formal agencies. In addition, there will be representation from key civic agencies, such as the Los Angeles County Board of Supervisors and the Los Angeles Mayor's Office ([name], and representatives from local neighborhood planning councils), as part of the advisory group for planning. This addition of grass-roots community members and civic leaders, helps make the overall project a community-wide project, supports the community-engagement model, and builds community support for implementation. These are public roles, but the participants are also research subjects because they will be asked to complete conference surveys; notes of planning meetings are project data; and training and planning meetings and conferences, may be attended by study research staff making observations and taking field notes as qualitative research data for the project. For these activities, the community leaders and advisors are also research subjects and will be asked to sign a consent form for participation in the research activities of the project. Community members will be recruited for their advisory roles by the lead CBOs for the project, through advertising among the community contacts for these roles. The Community members participating in these roles will receive thank-you stipends from the CBOs. The civic leaders will be recruited from the mayor's and Board of Supervisor offices (see support letters), with additional nominations from those offices and the lead CBOs, as they have broad knowledge of community leadership in their areas. Civic leaders will not receive a stipend for participating, as it is assumed to be within the scope of their usual duties.

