12 month follow-up survey. Between May 10, 2011 and March 12, 2012, we approached 974 participants for 12-month follow-up telephone survey; 272 enrolled participants were not attempted for 12-month follow-up based on their baseline or 6 month survey status. Of 974

attempted for 12-month follow-up, N=733 (75% of attempted, RS: 364, CEP: 369) completed the survey, 7 refused (RS: 4, CEP: 3), 229 were unable to contact (RS: 109, CEP: 120), and 5 deceased (RS: 3, CEP: 2).

3 year follow-up survey (extension study). Between 1/14/2014 and 10/14/2014, we attempted to contact 1004 participants for 36-month follow-up with exclusion who deceased (RS: 4, CEP: 4), who made final refusal in previous wave (RS: 22; CEP: 27), or who had no data on baseline, 6, and 12 months (RS: 84; CEP: 101). Of 1014 attempted for 36-month follow-up, 600 (600/1014=59%) participated (RS 293, CEP:307), 24 were deceased (RS:14, CEP:11), 10 refused (RS:7, CEP:3), 3 were too ill/incapable (RS:2, CEP:1), and 367 (RE:180, CEP:186) were not able to be reached.

4-year follow-up of the 3-year sample (extension study). The CPIC 4-year study was added to explore longer-term outcomes for the sample completing the 3-year follow-up, based on community stakeholder interest. In addition, this follow-up offered CPIC participants the opportunity to be participants in an additional project, the Community and Patient Partnered Research Network (CPPRN). Between 3/31/2016 and 5/26/2016, we attempted to contact 598 clients (RS: 292, CEP: 306) who completed CPIC 3 years interview participants excluding 2 that declined follow-up (RS 1, CEP 1). The telephone interview took about 15-20 minutes. At the end of the interview, a respondent was asked “Would you like to hear about the CPPRN program?” and “do you agree to be part of the CPPRN?” if answered ‘yes’. Of those, 283 (47.3%) participated (RS 143, CEP 140), with 308 not reached (RS 143, CEP 165), 1 deceased (RS 1, CEP 0), 5 refused (RS 5, CEP 0), and 1 too ill to participate (RS 0, CEP 1).⁵

A2. Weighting

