For all study components (including supplement components discussed below), we convened working groups co-chaired by academic and community members to review analysis plans, data output and discuss findings.

Analyses for 6-month outcome: We conducted intent-to-treat, comparative-effectiveness analyses with intervention status as the independent variable, using logistic regression for dichotomous measures and Poisson regression models for count variables. Covariates were selected to account for known associations of sociodemographic and clinical status indicators with primary outcome measures. We adjusted for baseline status of dependent variables and covariates (age, sex, ≥ 3 chronic general medical conditions from a list of 18, education, race/ethnicity, family income < federal poverty level, 12-month alcohol abuse or use of illicit drugs at baseline, 12-month depressive disorder at baseline, and community). All analyses were conducted using SUDAAN Version 10.0 (<http://www.rti.org/sudaan/>) and accounted for clustering (clients within programs), weighting, and multiple imputations. Significance of comparisons by intervention status was based on regression coefficients. Results of logistic regression models are presented as odds ratios (OR) and Poisson models as rate ratios (RR) with 95 % confidence intervals. We illustrate results for intervention groups adjusted for covariates using standardized predictions generated from fitted regression models.¹⁴ We present Cohen's effect size index h , defined for dichotomous variables,¹⁵ where $h=0.20$ is small, $h=0.50$ is medium and $h=0.80$ is large. We supplement adjusted models with unadjusted raw data to assess

robustness. We applied a Bonferroni adjustment considering two primary outcomes (Poor mental health qualify of life $MCS-12 \leq 40$, and at least mild depression $PHQ-9 \geq 10$) and compared the proportion of results across outcomes favoring one intervention to an assumed null-hypothesis of 0.5.

Analyses for 12-month outcome: We conducted intent-to-treat analyses of repeated measures including all participants with available data at baseline, 6-, or 12-months by using SAS software version 9.2 (SAS Institute). We used a model-based approach with unweighted data. Initial explorations of 3-level, random-effects logistic models using SAS PROC GLIMMIX for binary outcomes yielded unstable estimates for program-specific random effects.^{16, 17}

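### Only community-engagement agencies are given a role in analysing and preparing findings, from the end of 6-month rather than 12-month data collection, with no rule holding back by-arm results

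*Combined protocol and SAP*

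**What the plan says.** Section 8.1a (Agencies) describes 6- and 12-month client surveys in both conditions and then continues: "Following the 6-month outcomes data collection for the client study, the agencies in the community engagement condition will be asked to identify representatives to participate". What these representatives would take part in is set out next: "in collaborative analyses and preparation of findings for presentation at the Community Feedback Conference, attended by all participating Agencies". The sentence closes with recommendations and the start of wait-list training for the control agencies. Control agencies appear in it only as part of the conference audience and as recipients of that training.

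Section 8.1a (Community Leaders and Advisors) says of the intervention groups that key agency leaders take part in the four-month planning, help oversee implementation and "participate in the collaborative analyses of data from each stage". Four-month planning belongs to the Community Engagement and Planning (CEP) condition, so this most naturally means CEP leaders.

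Two other places describe the partners without naming an arm. The opening of Section 4 says: "After several months of collaborative analysis involving community agency partners, the project will sponsor a community feedback conference to share the outcomes findings". Appendix A4 reports that "we convened working groups co-chaired by academic and community members to review analysis plans, data output and discuss findings".

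Section 4.3 times the conference, not the analysis: the lead community organisations sponsor a "Community Feedback Conference at 40 months (after all client outcomes data are collected".

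Appendix A1 gives the fieldwork dates. The 6-month survey ran from 2 November 2010 to 11 August 2011. For the next wave: "Between May 10, 2011 and March 12, 2012, we approached 974 participants for 12-month follow-up telephone survey".

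**The concern.** Two things are at stake.

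**The 12-month comparison.** The hypothesis in Section 5 covers improvement over 6 to 12 months. CEP agencies implement for 12 to 18 months (Section 8.1a), so many would still be delivering the intervention when 6-month results became available. They are told which of their clients are enrolled, and a note in Section 4.3 says RS programs are not. Clients may learn their program's assignment from its staff (Section 4.2), and outcomes are self-reported (Section 7). Staff who knew a favourable or unfavourable 6-month result could change their effort toward identifiable panel members, or those clients' expectations, in one arm only. The 12-month model cannot remove such an effect.

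**Interpretation.** People who oversee delivery of CEP would help judge whether CEP did better than RS, with no RS counterpart. Parts of Section 5 leave room for judgement: covariates may be chosen by bivariate screening and model building, and multiplicity is assessed partly by the proportion of results favouring one intervention. The working groups in Appendix A4 reviewed analysis plans and data output, and no masking of arm labels is described.

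**Working it through.** The plan has no figure of its own to reproduce here. The check compares passages and counts days.

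**1. Who takes part**

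| Place | Who is named | RS role in analysis |
|---|---|---|
| 8.1a, Agencies | CEP agencies | None; audience and later trainees |
| 8.1a, Community Leaders and Advisors | Leaders in the intervention groups | None |
| Section 4, opening | Community agency partners, no arm | Not excluded, not stated |
| Appendix A4 | Community members, no arm | Not excluded, not stated |

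Where an arm is identified, it is CEP. The neutral passages neither give RS a matching role nor withdraw the one-arm wording.

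**2. When it starts**

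- Section 8.1a (Agencies): after 6-month collection. No latest date is given, and no wait for the 12-month wave.
- Section 8.1a (Community Leaders and Advisors): data from each stage, which fits staged access.
- Section 4.3: the conference waits for all client outcomes; the analysis is not mentioned.
- Section 9: protects identifiers but does not address release of by-arm results.

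**3. Possible overlap by the actual dates (Appendix A1)**

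- 12-month fieldwork, 10 May 2011 to 12 March 2012: 307 days.
- Of this, before 6-month fieldwork closed, 10 May to 11 August 2011: 93 days.
- Remaining, 11 August 2011 to 12 March 2012: 307 − 93 = 214 days, about 7 months.
- Share remaining: 214 / 307 = 70%. Counting both end dates gives 214 / 308 = 69%.

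These are calendar days. Interview dates are not given, so this cannot be turned into a share of the 733 completed 12-month interviews.

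**4. Possible sequence by the planned dates**

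Unit selection closes by month 13 (Section 4.1) and screening follows a conference by six months (Section 4). Assume kick-off at about month 13:

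- screening from month 13 + 6 = 19;
- 6-month surveys from month 19 + 6 = 25;
- 12-month surveys from month 19 + 12 = 31;
- conference at month 40, which is 40 − 31 = 9 months after 12-month surveys begin.

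Several months of analysis could fit after the 12-month wave, or could begin before it closes. Recruitment in batches makes the end of that wave uncertain. A note in Section 4 moves all timelines by one year, which leaves these gaps unchanged.

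**5. Wait-list training**

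The Agencies sentence lists the start of control training among activities that follow the 6-month wave. The opening of Section 8.1a, an earlier paragraph under Agencies, and the Clinicians text all place it after the trial. If the trial includes the 12-month survey, the two timings differ.

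**The case against.** The strongest reply is that the 6-month trigger times a request for names, not a release of results. Work begun after 12 March 2012 would also follow 6-month collection, and the planned timeline leaves room for that order. This stands: overlap is permitted, not stated.

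A reader might infer that Section 8.1a contradicts Section 4.3. It does not. One times the conference and the other the nomination of people whose work feeds it; both can be true.

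A reader might also infer that RS agencies were shut out throughout. The opening of Section 4 and Appendix A4 name no arm, and Section 4.1 says some agencies may have units in both conditions. The one-arm wording is confined to Section 8.1a.

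There are safeguards. Survey staff were blinded, the study did not tell clients their assignment, the primary measures were designated during the design phase, and Section 5 lists the main-model covariates. The 6-month outcomes themselves cannot be altered by anything disclosed after they were collected. These points reduce the risk. Interviewer blinding, however, does not reach staff effort or client expectation, and early designation of measures does not settle who interprets the results.

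Finally, collaborative analysis is part of the declared participatory framework. That supports involving community partners; it does not explain why the partners named come from one arm.

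**Conclusion.** The concern holds as a gap in the rules for access to results. Section 8.1a gives a stated analysis role to one arm and ties it to the 6-month wave. No passage gives RS a matching role or holds back by-arm results until 12-month collection closes.

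The exposure is at most 214 of 307 calendar days (70%). Reaching that limit would require release on the day 6-month fieldwork closed, before weighting and imputation were done. The figure should not be read as 70% of 12-month data being affected. The documents show no early disclosure and give no basis for sizing a bias.

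The 6-month trigger may be left over from budget changes: the Introduction says the 12-month outcomes were dropped and later restored. That would explain the wording but not remove the need to correct it. The timing of wait-list training must be reconciled as well. No sample size or power figure changes.

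**What to change.** Amend both Section 8.1a passages, and align Section 4 and Appendix A4 with them, so that:

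- no by-arm client results leave the analysis team until 12-month fieldwork closes;
- representatives of both arms, or of neither, are invited to collaborative analysis;
- working groups see output with arm labels masked until outcome definitions and models are fixed;
- the statements on when wait-list training of controls begins are reconciled.

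If by-arm results were seen earlier, report the date and who had access, as a limitation. Splitting 12-month effects at that date would not be a clean check: interview date follows enrolment date, and agencies were recruited in batches, South Los Angeles before Hollywood, so the split would be confounded with batch and community.

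The cost is protocol wording and a delay of up to about seven months in agency access to the analysis. The conference is unaffected, because Section 4.3 already holds it until all client outcomes are collected.

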8.2. ADEQUACY OF PROTECTION AGAINST RISKS

8.2a. Recruitment and Informed Consent

Lead administrators from the participating agencies will be asked to review a description of CPIC on the web survey, and will review that description with appropriate leaders within their agency. Agencies will submit a signed letter to initiate their participation. The composition and recruitment procedures are provided in detail above, but briefly include agencies participating in the Community Partnership Initiative; and additional primary care and specialty care agencies identified by social service agencies as their main partners of that type. There will be 80 organizations that participate. The organizations will be invited by mail to enroll as a participating agency and the subsequent study activities. Organizations will be free not to participate.

Administrators and Clinicians: We will ask each participating agency to identify 1 administrator, supplemented in agencies with organizational units in both intervention conditions, by administrators that support the additional intervention, for an approximate sample of 100 administrators. Administrators identify organizational units with full time clinicians/case workers for adults, and these units will be arrayed by the study to select 50-60 for random, stratified assignment to the intervention conditions in the main study. To have alternative sites and due to the timing of obtaining the information to select units and recruiting clinicians, we expect to have some clinicians participating in units that are not selected for the study.

Clinicians/Case Workers: Using lists of all full-time clinicians or case workers for adults within selected units, we will use recruitment packets and follow-up calls to recruit 5 clinicians per unit, replacing as necessary from remaining clinicians; and if necessary replacing units with others from the remaining nonselected pool. In PIC, all but 2 clinicians agreed to participate in selected clinics, so we expect a similarly high rate here given high agency interest and cooperation. We expect 200-250 clinicians in the 60 main study units and another 100-150 from other units. Clinicians will be free to choose not to participate in the study or in particular activities of the study.

Clients: We will recruit a consecutive sample of adult clients visiting participating clinicians, over a two week period for that site. Following posting of notices for the study or sending fliers, the agency's staff will ask their clients if they are interested in participating in a research project in which the agency is participating. If the client is interested, he/she will be directed to see the RAND field staff person assigned to that agency. We hope to talk to 6000 clients across the 48 units, and expect to complete 4200 screeners. Those with a positive

depression score, an estimated 840, will be asked to complete a baseline survey at the agency or if this is not feasible, in a follow-up telephone call. An estimated 500 will agree to the survey and sign consent forms to participate in the study. The field staff who do the screening give the client a written study summary and a question and answer booklet, review these materials with the client, and get written consent from the client. In addition, clients will be asked to give permission for their clinician to complete a post-visit report. Enrolled, depressed clients will also be asked to consent to a 6-month follow-up telephone survey and a 12-month survey. We expect 500 enrolled participants to complete the 6-month interview and 470 to complete the 12-month survey. Clients are free not to participate, receive referrals to mental health providers whether or not they are in the higher intensity condition, and all clients will be free to accept treatments or referrals or not.

8.2b. Protection against Risk

Subjects will know that they are free to refuse to participate in each stage of the study, and to leave questions or issues unanswered. Subjects will know that they will have the option of completing a survey at the agency or by telephone. If a life-threatening situation is encountered during the telephone interview or other contact with participants, emergency protocols similar to those developed for PIC will be followed. For example, for life-threatening physical emergencies, subjects are instructed to call 911 and assisted if necessary. The main other emergencies are a patient becoming disoriented or severely confused, or disclosing that they are currently suicidal. Project interviewers will be trained in protocols for contacting the project on-call physician who can make contact with the participant and/or provide referrals to a specific doctor or clinic identified for this purpose within each geographical area. During PIC telephone interviews there were no instances where interviewers encountered life-threatening physical health situations. However, there were about 2 instances per survey wave where the interviewer was concerned because a subject suggested they might have been recently suicidal (out of about 1000 interviews per wave). Following the approved protocol, the study PI contacted these participants (usually within 24 hours or as soon as they could be reached by telephone) and discussed the situation. In all instances, the patients were well aware of their options for treatment, all were in active treatment, and all were discussing their symptoms with their providers and felt they did not need additional assistance contacting their doctor. Most subjects

in this category had already seen their provider that day or were scheduled to see their provider the following day. All appreciated the contact by the PI.

Responding to mental health emergencies by telephone is challenging, particularly at some distance where there is no current rapport with a treating provider, or where there is no active treatment provider. Because of this, we will increase the chances the subjects will have information needed to avoid emergencies. In our recently completed 8-year follow-up of PIC participants, we had no telephone emergencies. To assure responsiveness in the case of an emergency, we developed a protocol to have test the PI's responsiveness by having calls at random times, and the response to the telephone center was within 2 minutes over 10 calls.

All patient-identifying information will be kept confidential. RAND's Survey Research Group (SRG) will use one set of identifiers (Field IDs) in their contacts with participants. Our senior programmer will receive field data from SRG and transform the Field IDs to another set of IDs (Analytic IDs) before the data are available to the investigators. The file that links the 2 IDs will be secured and accessible only to the senior programmer and RAND's privacy office. Identifiable hard copy data will be maintained separately by SRG with limited access and kept only as long as needed to maintain consent files or to contact patients for follow-up surveys. A detailed data safeguarding plan will be developed for the study and submitted to the IRBs at RAND and UCLA for approval. See section on Data and Safety Monitoring Plan below.

All field staff who interact with clients will receive at least 4 days of paid training at RAND and are required to complete the UCLA online course for social behavioral training in the protection of human subjects. General training includes general interviewing skills such as maintaining neutrality and use of non-leading probes, use of the interview software, SRG confidentiality, data safeguarding and quality control policy and procedures, and how to handle emergency situations such as intent to harm self or others. During PIC clinician training, clinicians are encouraged to review potential side effects of treatments with patients, and to elicit their treatment preferences and negotiate with clients to receive their treatments of choice.

